### **1.14 Planned analysis**

The primary analysis will be conducted under the ITT principle using modified ANCOVA as described above. Raw and adjusted mean differences in PFG at week 6 between the intervention and control arm will be presented with 95% confidence interval (95% CI). The adjusted mean difference will be estimated using a linear regression model of week 6 FPG to baseline PFG and treatment arm adjusted for age and sex.

The primary null hypothesis is of no difference in week 6 FPG adjusted means between the intervention and the control arms. It will be tested against the alternative hypothesis of a difference between the two groups.

$$H_0: \mu_0 = \mu_1$$

$$H_A: \mu_0 \neq \mu_1$$

Where  $\mu_0$  and  $\mu_1$  are the week adjusted trimmed mean FPG in respectively the control and intervention group. The null hypothesis will be rejected if the robust adjusted 95% CI of the mean difference does not include 0.

- Power of the analysis

With 60 participants in each group and assuming that the average PFG changes from baseline to the week 6 will be -0.6 mmol/l in the intervention arm and -0.1 mmol/l in the control arm, that the baseline standard deviation (sd) of PFG is 0.7, the post-intervention sd is 0.6, and that the correlation between baseline and post-intervention measurement range between 0.6 and 0.4, the analysis will have a power greater than 0.9 to detect a difference between both arms.

- Sub-group and additional analysis of the primary outcome

An interaction between baseline FPG and treatment effect will be tested.

No sub-group analysis is planned for the primary endpoint.

- Sensitivity analysis

The robustness of the results will be tested using a non-parametric model as described above.

Both results will be presented and discrepancies will be discussed.

## **Secondary endpoints**

The same analyses (described in the method section and detailed for week 6 FPG above) will be computed for all of the following continuous variables. Therefore, only additional specific analyses are described in the section below.

### **1.15 Variables related to glucose regulation:**

Participants are scheduled to have an OGTT at baseline (visit 3), weeks 6 (visit 6), week 12 (visit 8) and week 26 (visit 10).

- Fasting Plasma glucose
  - Derivation: plasma glucose after a 12 hours fast and before the 75g glucose load will be measured via an OGTT.
  - Analysis: modified ANCOVA and LMM; no additional analysis.
- Plasma glucose at 120 minutes following 75g OGTT (G120)
  - Derivation: Plasma G120 minutes after 75g glucose load will be measured via an OGTT.
  - Analysis: modified ANCOVA and LMM; no additional analysis.
- HbA1c will be measured by the Pathology Department in Hammersmith Hospital (Imperial College Healthcare NHS Trust).
  - Analysis: modified ANCOVA and LMM; no additional analysis.
- Insulin resistance index computed using the Homeostasis model assessment (HOMA) of beta cell function

- Derivation: the insulin resistance index (IRI) will be derived using the HOMA mathematical model. It requires the FPG and fasting insulin concentration and is computed as follows:

$$IR = \frac{glucose \times insulin}{22.5}$$

where glucose stand for FPG in mmol/l and insulin for fasting insulin in mU/l.

- Analysis: modified ANCOVA and LMM; no additional analysis.
- C-peptide at 120 minutes following 75g OGTT will be measured by the Pathology Department in Hammersmith Hospital (Imperial College Healthcare NHS Trust).
  - Analysis: modified ANCOVA and LMM; no additional analysis.

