TITLE Assessment of the Impact of a Personalised Nutrition Intervention in Impaired Glucose Regulation

DESIGN Pilot Study;

Allocation: RCT

Intervention model: Parallel assignment with an active control

Masking: None

Primary purpose: Prevention

AIMS • To compare the impact of a DNA-based diet on glucose regulation in prediabetic individuals with that of standard care.

OUTCOME MEASURES Primary outcome (measured at 6 weeks):

- Difference in 0 minutes glucose on 75g oral glucose tolerance test between the control arm and the intervention arm.

Secondary outcomes:

- Cross-arm and within arm differences (compared to 0 week measurements) between the control arm, intervention arm, and the exploratory arm, in respect of:
 - 120 minutes glucose on 75g oral glucose tolerance test
 - 0 minutes glucose on 75g oral glucose tolerance test
 - HbA1c
 - Weight
 - BMI
 - Lean mass
 - Fat mass
 - Waist circumference
 - Total cholesterol
 - Fasting Triglycerides
 - LDL cholesterol
 - HDL cholesterol
 - HOMA Insulin sensitivity and secretion measurement
 - 120 minute c-peptide following 75g oral glucose tolerance test
 - Systolic blood pressure
 - Diastolic blood pressure
 - Food frequency (by food frequency questionnaire (FFQ) and 24hour recall)
 - Energy intake
 - Carbohydrate intake

- Fat intake
- Saturated fat intake
- Salt intake
- Vitamin D
- Vitamin B6
- Vitamin B12

All of the above secondary outcomes will be measured at 6 and 12 weeks, and a follow-up at 26 weeks (with the exception of HbA1c which will only be measured at 12 and 26 weeks).

- The number of participant withdrawals during the trial.

POPULATION Adults with impaired glucose regulation defined by impaired fasting glucose (IFG) or impaired glucose tolerance (IGT) in line with WHO criteria (N = 180).

ELIGIBILITY Inclusion criteria:

- Adults over 18 years of age
- Impaired glucose regulation including IFG and IGT by fasting glucose, OGTT or HbA1c criteria
- Access to smartphone with an operating system of iOS 8.0 or above, or Android 4.0 or above.

Exclusion criteria:

- Diabetes
- Pregnant or planning pregnancy
- Breastfeeding
- Enrolled in other clinical trials
- Have active malignancy or under investigation for malignancy
- Severe visual impairment
- Reduced manual dexterity
- Use of psychiatric, anti-diabetic, and/or weight loss medication, and/or oral steroids
- Bariatric surgery

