4 PARTICIPANT ENTRY

4.1 PRE-REGISTRATION EVALUATIONS

Potential participants will undergo a screening process prior to entry into the study. Potential participants will be invited to the clinical research facility where they will be talked through the consent procedure and allowed to ask any questions they may have. Following consent and verification that they are eligible via the inclusion and exclusion criteria, they will undergo a glucose regulation test via finger prick blood sample that will be analysed either via a point of care (POC) HbA1c test, or a lab analyser, to measure HbA1c. The lab analyser (TOSOH G8 analyser) will be used to assess HbA1c on a capillary sample if the Siemens DCA Vantage Analyser POC device is unavailable or returns values that are out of the acceptable range for accuracy. Both devices will be used in line with manufacturer instructions. If a participant is found to be type 2 diabetic they will be referred to their GP for further care.

The HbA1c test results will be interpreted according to WHO criteria:

- HbA1c below 42 mmol/mol (6.0%): Non-diabetic
- HbA1c between 42 and 47 mmol/mol (6.0–6.4%): IGT – Pre-diabetic
- HbA1c of 48 mmol/mol (6.5%) or over: Type 2 diabetic

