6 STUDY PROCEDURES AND SCHEDULE

6.1 STUDY PROCEDURES/EVALUATIONS

6.1.1 STUDY SPECIFIC PROCEDURES

The following list of procedures will be performed on all participants:

- Medical history - Participants will be asked a series of questions by the research nurse to ensure that they do not meet any of the exclusion criteria of the study.
- Genetic testing – saliva samples will be provided.
- Physical examination – Assessment of weight, height, waist circumference, blood pressure, lean mass, fat mass.
- Hematology – blood test to examine total cholesterol, HDL cholesterol, LDL cholesterol, fasting triglycerides, HbA1c
- Biological specimen collection – saliva samples will be obtained via the collection of 2ml of spit per sample. Another saliva sample will be provided by means of a buccal cheek swab, to be used in conjunction with the NudgeBox.
- Insulin sensitivity – 0 minutes on 75g glucose OGTT, 120 minutes on 75g glucose OGTT, 120 minutes c-peptide following 75g glucose OGTT, HOMA insulin sensitivity and secretion measurement
- Pregnancy test
- Food frequency questionnaire
- Trial commencement and completion questionnaires

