6.2 STUDY SCHEDULE

6.2.1 SCREENING

Visit 1: Study preparation

- Send participants a Participant Invitation Letter (Appendix 8), and PIS (Appendix 6).
- Schedule a screening visit for potential participants.

Visit 2: Screening (Day -42 to -0 +/-10 working days)

- Discuss the consent procedure (Appendix 5) and any questions that a potential participant may have regarding the trial.

- If the potential participant would like to participate in the trial, they will be provided with an opportunity to sign the consent form and the PIS. A copy of the consent form will be provided to the participant and a copy will be retained by the clinical trial team.
- Review medical history to determine eligibility based on inclusion/exclusion criteria.
- Perform medical examinations needed to determine eligibility based on inclusion/exclusion criteria. This will include a finger prick blood sample that will be analysed either using a point-of-care HbA1c test using a Siemens DCA Vantage POCT device, or a lab analyser, to measure HbA1c levels.
- Send the GP letter (Appendix 7) to the GP of each confirmed participant in the trial who has consented to informing their GP of their participation in the trial.
- Provide participants with access to online and/or hard-copy food frequency questionnaire that they will need to complete for 1 week of food intake prior to their first clinical appointment in the trial (Visit 3).

Following confirmed enrolment in Visit 2, participants will undergo assignment to one of the three arms of the study.

Visit 3: Baseline clinical measurements (Day -21 +/- 10 working days)

- Verify inclusion/exclusion criteria and consent.
- Perform clinical assessment of glucose regulation and anthropometric measurements.
- Obtain urine pregnancy test (if applicable).
- Collect blood sample (15mL).
- Assess blood pressure, weight, height, waist circumference, lean body mass, and fat body mass.
- Perform 0 minutes on 75g glucose OGTT, 120 minutes on 75g glucose OGTT, 120 minutes c-peptide following 75g glucose OGTT, HOMA insulin sensitivity and secretion measurement.
- Provide two saliva samples (2mL each) via spit.
- Complete trial commencement questionnaire.

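### The SAP points to the Visit 2 finger-prick screening HbA1c as baseline, although endpoint HbA1c is a hospital laboratory assay; within-arm change could shift without any treatment effect

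*SAP*

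**What the plan says.** **Baseline source.** Table 1 in SAP section 1.8 (baseline variables) gives the Visit 2 CRF as the source for HbA1c. Weight, blood pressure, glucose, C-peptide and lipids in the same table come from the Visit 3 CRF.

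**What Visit 2 is.** It is the screening visit. Protocol 6.2.1 says of the eligibility examinations: "This will include a finger prick blood sample that will be analysed either using a point-of-care HbA1c test". Protocol 4.1 describes the sample as "analysed either via a point of care (POC) HbA1c test, or a lab analyser, to measure HbA1c". The second device is a backup, for when the point-of-care device is unavailable or its reading is outside its accuracy range: "The lab analyser (TOSOH G8 analyser) will be used to assess HbA1c on a capillary sample". The result is then classified, with the eligible band given as "HbA1c between 42 and 47 mmol/mol (6.0–6.4%): IGT – Pre-diabetic".

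**Endpoint source.** SAP section 1.15: "HbA1c will be measured by the Pathology Department in Hammersmith Hospital". The protocol Study Summary places HbA1c follow-up at two visits, "with the exception of HbA1c which will only be measured at 12 and 26 weeks".

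**Planned use of baseline.** The protocol Study Summary lists, as secondary outcomes, "Cross-arm and within arm differences (compared to 0 week measurements"). SAP section 1.5 includes changes from baseline, section 1.9 gives a change-score model, and section 1.15 assigns ANCOVA and the mixed model to HbA1c.

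**Room for a laboratory baseline.** Protocol 6.1.1 lists, for all participants, a "blood test to examine total cholesterol, HDL cholesterol, LDL cholesterol, fasting triglycerides, HbA1c", without saying at which visit. Protocol 6.2.1 draws 15 mL of blood at Visit 3 without listing the assays.

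**The concern.** Two things can move a within-arm change when the baseline is the screening value.

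- **Regression to the mean.** The reading that admits a participant carries measurement error. Conditioning on that reading falling in a window makes its average error non-zero among those admitted. The next, unselected reading does not share that error.
- **Method difference.** The screening value is capillary and may come from either of two devices, chosen partly by the reading itself. The endpoint value comes from the hospital laboratory. Neither document gives an agreement check or calibration.

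At stake are the within-arm HbA1c change in the protocol and, if the Visit 2 value enters the mixed model as time zero, its time trend. With follow-up only at weeks 12 and 26, every HbA1c change depends on this one baseline. The between-arm comparison is at risk only through lost precision.

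**Working it through.** The documents give no SD, reliability, power or sample size for HbA1c, so there is no figure of the plan's to reproduce. The eligibility window (42 to 47 mmol/mol) and 60 participants per arm come from the protocol. Every other HbA1c input below is an assumption, shown as a range.

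**1. Regression to the mean**

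Let the screening value be X = T + e, with T the true level (mean m, SD 4 to 5) and e the screening error (SD 1 to 2). Reliability is R = SD²/(SD² + error SD²). Selection is on X from 41.5 to 47.5, that is, 42 to 47 in whole numbers. With no treatment effect and no device offset:

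expected change = -(1 - R) × (mean of X among those selected - m)

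The mean of X among those selected is a truncated-normal mean.

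- m = 40, SD 4, error 2: R = 16/20 = 0.80; selected mean 43.88; change = -0.20 × 3.88 = -0.78.
- m = 42, SD 5, error 1: R = 25/26 = 0.962; selected mean 44.23; change = -0.038 × 2.23, about -0.09.
- m = 44, SD 4, error 2: selected mean 44.43; change = -0.20 × 0.43 = -0.09.
- m = 46, SD 4, error 2: selected mean 44.71; change = -0.20 × (-1.29) = +0.26.

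Over the whole grid:

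| Screened mean (mmol/mol) | Change with no treatment effect (mmol/mol) |
|---|---|
| 40 | -0.78 to -0.15 |
| 42 | -0.43 to -0.09 |
| 44 | -0.09 to -0.02 |
| 46 | +0.05 to +0.26 |

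The sign depends on whether the screened population's mean lies below or above the mean of those selected, because the window is cut on both sides. In this model a Visit 3 laboratory baseline gives zero expected change, because its error played no part in selection.

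**2. Device offset, and within-arm against between-arm**

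Simulation: 60 per arm, 4,000 runs, no true effect, screened mean 40, true SD 4.5, screening error SD 1.5, laboratory error SD 1.0.

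| Laboratory offset (mmol/mol) | Mean within-arm change | 5% within-arm test rejects |
|---|---|---|
| 0 | -0.41 | 41% |
| +1 | +0.59 | 70% |
| -1 | -1.40 | 100% |
| -2 | -2.41 | 100% |

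The offset adds one-for-one. In the same runs the between-arm difference stays within 0.01 of zero. Rejection is 4.2% to 4.8% for change scores and 4.3% to 5.0% for ANCOVA. Two limits apply: the ANCOVA was fitted by least squares, not by the SAP's robust estimator, and no true within-person change was simulated. Adding such change would widen the intervals and lower the within-arm rejection rates.

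**3. Precision of the between-arm ANCOVA**

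Residual variance ratio = (1 - r² for the screening baseline)/(1 - r² for a Visit 3 laboratory baseline), where r is the correlation with follow-up and both values are taken from the same scenario.

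- With no true within-person change the ratio runs from about 1.1 to 2.4.
- With an assumed within-person change SD of 2 mmol/mol it is roughly 1.04 to 1.45.

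An example shows why it shrinks. With SD 5 and screening error 2, residual variance given the screening value is 25 × 4/29 + 1 = 4.45. A ratio of 2.4 implies 4.45/2.4 = 1.85 given a laboratory baseline. Adding a change variance of 2² = 4 to both gives 8.45/5.85 = 1.44.

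**The case against.** **The table may not define the analysis baseline.** It is introduced as a descriptive summary by arm, and sections 1.9 and 1.15 name no visit for baseline HbA1c. It is also imperfect as a list of analysis baselines: it shows 120-minute insulin and time-zero C-peptide, whereas the endpoints use fasting insulin and 120-minute C-peptide. This stands as a caution. But no other place in either document gives the source of baseline HbA1c, so an analyst would start from this table.

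**A laboratory baseline may already exist.** A reader might infer that mixing of devices is established. The documents do not support that. The sentence in section 1.15 is not limited to follow-up visits, HbA1c is in the general blood panel, and blood is drawn at Visit 3. Mixing follows only from reading the baseline table against section 1.15. The SAP needs correcting in both cases: if the Visit 3 assay is run, the table points to the wrong value; if it is not, there is no like-for-like baseline.

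**The direction is not fixed.** A reader might infer that HbA1c will appear to fall. That does not follow. Several recruitment routes in protocol 4.4 draw on a registry of people already identified as prediabetic, so a screened mean inside the window is realistic, and there the drift is near zero or positive. A device offset could also go either way.

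**Selection is not strictly on HbA1c.** The inclusion criteria also admit by fasting glucose or OGTT. However, HbA1c is the only glucose test described at screening, and the OGTT is at Visit 3, after assignment to an arm.

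**Planned inference is mostly between arms.** This is correct. SAP section 1.5 defines its secondary endpoints between arms. The within-arm outcome is in the protocol Study Summary, with no test specified.

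**Conclusion.** The point holds as a defect in how baseline HbA1c is sourced. The one place that gives a source names a selected capillary screening value, while the endpoint assay is the hospital laboratory's.

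If that value is used, within-arm change and the mixed-model time trend may shift with no treatment effect: about -0.8 to -0.1 mmol/mol from regression to the mean at screened means of 40 to 42, near zero at 44 and slightly positive at 46, plus any device offset in full. These sizes rest on the assumed SDs and screened means and cannot be fixed from the documents.

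A reader might infer that the treatment comparison is biased. It is not: randomisation makes drift and offset equal across arms in expectation, for both ANCOVA and change scores. The cost there is precision. Its upper figure of about 2.4 needs a true HbA1c that does not change within a person; roughly 1.04 to 1.45 applies if it changes with SD 2 mmol/mol. This is one secondary outcome, and the remedy is nearly free.

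**What to change.** In SAP section 1.8 (the baseline-variables table) and section 1.15, define baseline HbA1c as the Visit 3 venous sample, measured by the same Pathology laboratory as weeks 12 and 26. State that the Visit 2 value is used for eligibility only and does not enter the change, ANCOVA or mixed models.

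The cost is SAP wording and, if HbA1c is not already run on the Visit 3 blood, one assay per participant on a sample already drawn.

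If a Visit 3 laboratory value cannot be obtained, restrict HbA1c inference to between-arm contrasts, record which screening device produced each Visit 2 value, and report any within-arm change as descriptive, with the reason stated.

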## 1.16 Variables related to anthropometric measurements

Patients are scheduled to have anthropometric measurements at baseline and visits 4, 6, 8 and 10 (weeks 6, 12 and 26).

- Body weight
  - Derivation: weight will be recorded in light clothing without shoes to the nearest kilogram using the same scale during the trial
  - Analysis:
    - Main analysis: modified ANCOVA and LMM.
    - In addition, changes in weight over time will be analysed using a LMM model first with measurements taken at weeks 4, 6, 12 and 26.
- Body Mass Index (BMI)
  - Derivation: height will be measured bare foot to the nearest 1 cm using a stadiometer. BMI will be computed as
 
$$BMI = \frac{weight(kg)}{height^2(m)}$$
  - Analysis:
    - Main analysis: modified ANCOVA and LMM.
    - Changes in BMI over time will be analysed using a LMM model first with only weight measurements taken at weeks 6, 12 and 26 then with all data including weight reported by phones
- Lean mass

- Derivation: lean mass will be measured using Bioelectrical Impedance Analysis with the Body Composition Analyser Tanita BC-418
  - Analysis: modified ANCOVA and LMM; no additional analysis.
- Fat mass
  - Derivation: fat mass will be measured using Bioelectrical Impedance Analysis with the Body Composition Analyser Tanita BC-418.
  - Analysis: modified ANCOVA and LMM; no additional analysis.
- Waist circumference
  - Derivation: waist circumference will be measured with to the nearest 0.5 cm at the midpoint of lower border of the costal margin and uppermost border of iliac crest using a non-stretchable measuring tape. Three consecutive measurements will be recorded.
  - Analysis: modified ANCOVA and LMM; no additional analysis.

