6.2.2 FOLLOW-UP

For sample scripts for all interactions with the dietitian for each arm of the study, see Appendices 9 (control arm), 10 (intervention arm), and 11 (exploratory arm).

Visit 4: Initial consultation with a dietitian (Day 0 +/- 6 working days)

- Perform 30-60 minute consultation with the dietitian
- Perform 24-hour recall of food intake for each participant.
- **Intervention and exploratory arms:** Provide NudgeBox experience whereby the participant will provide a buccal cheek swab to perform on-site rapid genotyping. This will provide the participant with a visualisation of how some of their genetic information is analysed

- **Control arm:** Provide NICE guidance by verbal and written communication as per standard care.
- **Intervention arm:** Provide DNA-based dietary information in verbal and written form to participants.
- **Exploratory arm:** Provide DNA-based dietary information via the DnaNudge App.

Visit 5: Follow-up phone-call with the dietitian (Day 14 +/- 6 working days) (Control and intervention arms only)

- Contact participants for a brief phone-call with the dietitian to address any dietary questions/problems.
- Perform 24-hour recall of food intake for each participant.

Visit 6: Glucose regulation review (Day 42 +/- 6 working days)

- Perform clinical assessment of glucose regulation and anthropometric measurements.
 - Obtain urine pregnancy test (if applicable).
 - Collect blood sample (15mL).
 - Assess blood pressure, weight, height, waist circumference, lean body mass, and fat body mass.
 - Perform 0 minutes on 75g glucose OGTT, 120 minutes on 75g glucose OGTT, 120 minutes c-peptide following 75g glucose OGTT, HOMA insulin sensitivity and secretion measurement.
 - Provide saliva sample (2mL) via spit.
- Complete FFQ

Visit 7: Follow-up phone-call with the dietitian (Day 56 +/- 6 working days) (Control and intervention arms only)

- Contact participants for a brief phone-call with the dietitian to address any dietary questions/problems.
- Perform 24-hour recall of food intake for each participant.

Visit 8: Glucose regulation review (Day 84 +/- 6 working days)

- Perform clinical assessment of glucose regulation and anthropometric measurements.
 - Obtain urine pregnancy test (if applicable).
 - Collect blood sample (15mL).
 - Assess blood pressure, weight, height, waist circumference, lean body mass, and fat body mass.

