6.2.6 SCHEDULE OF EVENTS TABLE

Activity	Trial Visit											Additional information
	1	2	3	4	5	6	7	8	9	10	11	
Send information documents to potential participants	x											
Consent		x										
Screening visit to assess glucose regulation		x										
Randomisation	x											
Fill in food frequency questionnaire	x				x		x		x			
Trial commencement questionnaire			x									All participants
Perform baseline measurements		x										
Take saliva sample for genetic testing (PCR)		x										
Initial consultation with dietitian			x									
Perform NudgeBox genetic test		x										
Provided with the DnaNudge App		x										Exploratory arm only
Follow-up phone-call with dietitian			x		x		x		x			Control and intervention arms
Perform 24-hour food recall		x	x		x		x		x			Control and intervention arms
6-week glucose regulation review				x								
Take saliva sample for leptin testing	x		x		x		x		x			
12-week glucose regulation review						x						
Trial completion questionnaire						x		x				
26-week glucose regulation review								x				
Weight measurement	x		x		x		x		x			
Height measurement	x		x		x		x		x			
Body composition	x		x		x		x		x			
Waist measurement	x		x		x		x		x			
Blood pressure	x		x		x		x		x			
Saliva sample (s)	x		x		x		x		x			
Venous blood test	x		x		x		x		x			
OGTT	x		x		x		x		x			
Pregnancy test (if applicable)	x		x		x		x		x			
Follow-up clinical visits				x		x		x				

Table 1: Schedule of events table for a trial participant.

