## 1.9 Analyses of quantitative data

Continuous outcomes will be compared between groups using the modified analysis of covariance (ANCOVA). This approach has been chosen because it is more powerful than other alternatives such as t-test.

A linear regression model will be used to analyse the association between post-intervention values of the outcomes with intervention arm adjusting for their baseline value, participant age and sex.

Let  $y_{it}$  denote the outcome value for individual  $i$  at time  $t$ ,  $x_i$  her covariates (e.g. sex, age) and  $d_i$  her intervention arm. The ANCOVA model is given by:

$$y_{it} = \beta_0 + \beta_1 y_{i0} + \beta_2 x_i + \gamma d_i + \varepsilon_{it}$$

An extension of the basic ANCOVA model will consider an interaction between the intervention indicator and the baseline values to test the assumption that the treatment effect varies with baseline status.

In addition, changes in continuous outcomes from baseline will be analysed using a linear regression model of the difference between the outcome value at visit and its baseline value. Using the same notation, the change model is

$$\Delta y_{it} = y_{it} - y_{i0} = \beta_0 + \beta_1 x_i + \gamma d_i + \varepsilon_{it}$$

Covariates will be centered in the analyses. Robust linear regression *lmrob* from the R package *robustbase* will be used for the ANCOVA analysis unless specified otherwise. It uses the MM-estimator to estimate the regression coefficient accounting for departure from normality of the outcomes.

Assessment of models' goodness of fit will include careful examination of residuals using graphical methods (scatter plot, boxplot and QQ plot) and detection of outliers. In addition, equality of the post-treatment variances will be tested using Levene's test.

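### SAP 1.16 rounds weight to whole kilograms and does not say which height enters follow-up BMI, which costs avoidable precision on weight and BMI change

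*SAP*

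**What the plan says.** SAP 1.16 gives the recording rules for the two inputs to BMI. For weight: "weight will be recorded in light clothing without shoes to the nearest kilogram using the same scale during the trial". For height: "height will be measured bare foot to the nearest 1 cm using a stadiometer". BMI is then weight divided by height squared, with no statement of which height is meant after baseline.

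The protocol lists the same measurements at baseline (6.2.1, Visit 3), at Visits 6 and 8 (6.2.2) and at Visit 10 (6.2.3): "Assess blood pressure, weight, height, waist circumference, lean body mass, and fat body mass". The schedule of events (6.2.6) has a separate row for height. So a fresh height is available at each clinical visit.

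For both weight and BMI the SAP states "Main analysis: modified ANCOVA and LMM". SAP 1.9 adds, for continuous outcomes, a "linear regression model of the difference between the outcome value at visit and its baseline value". For BMI there is a further step: "Changes in BMI over time will be analysed using a LMM model first with only weight measurements taken at weeks 6, 12 and 26". The same model is to be fitted a second time on a wider data set, which the SAP describes as "then with all data including weight reported by phones". The protocol lists no height measurement at any phone contact.

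**The concern.** Weight and BMI are secondary endpoints assessed over 6, 12 and 26 weeks, a period in which changes of one to a few kilograms are plausible. Rounding to whole kilograms adds error of a size that matters on that scale.

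The height question matters more for BMI. Adult height is effectively constant over 26 weeks, so a difference in recorded height between two visits is essentially measurement error. If same-visit height is used, that error passes into BMI change. A person of 86.7 kg has a BMI of 30.0 at 1.70 m and 29.65 at 1.71 m, a shift of 0.35 kg/m², about what 1 kg of weight would produce. Weight and BMI could then disagree in the same participant for no biological reason.

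The phone-reported weights make the gap concrete. Those BMI values must borrow a height from another visit. Without a rule, one longitudinal model could mix borrowed and re-measured heights.

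**Working it through.** The documents give no SD, variance or power for weight or BMI, so there is no stated figure to reproduce.

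**Inputs from the documents**
- Weight resolution 1 kg and height resolution 1 cm (SAP 1.16).
- Height measured at Visits 3, 6, 8 and 10 (protocol 6.2).
- 60 participants per arm (protocol 9.2).

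**Inputs assumed**
- SD of true weight change, s: 1.5 to 5 kg.
- SD of a repeated height reading, e: 0.2 to 0.5 cm.
- A typical participant of 88 kg and 1.70 m, so BMI = 88/2.89 = 30.45.

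**Step 1: weight rounding alone.** Rounding to 1 kg adds error variance of 1/12 kg² per reading, or 1/6 kg² to a difference of two readings. Relative inflation = (1/6)/s²:
- s = 1.5: 0.1667/2.25 = 7.4%
- s = 2: 0.1667/4 = 4.2%
- s = 3: 0.1667/9 = 1.9%
- s = 4: 0.1667/16 = 1.0%
- s = 5: 0.1667/25 = 0.7%

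With one fixed height, BMI change is weight change times a constant, so the same percentages apply to BMI.

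**Step 2: add same-visit height.** The sensitivity of BMI to height is 2 × 30.45/170 = 0.358 kg/m² per cm; squared, 0.128. The variance of true BMI change is about (s/2.89)². The added inflation is about 0.128 × (2e² + 1/6)/(s/2.89)². The 1/6 is the rounding of two heights, treated as independent.

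Example, s = 2 and e = 0.3: 0.128 × (0.18 + 0.1667)/0.479 = 9.3%. Adding 4.2% for weight gives 13.5%.

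Total inflation of the variance of BMI change:

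| s (kg) | e = 0.2 cm | e = 0.3 cm | e = 0.5 cm |
|---|---|---|---|
| 1.5 | 19% | 24% | 39% |
| 2 | 11% | 13-14% | 22% |
| 3 | 5% | 6% | 10% |
| 4 | 3% | 3% | 5-6% |
| 5 | 2% | 2% | 3-4% |

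Simulation at the same body size, against one baseline height with weight to 0.1 kg, agrees: variance ratios of 1.18-1.40 (s = 1.5), 1.10-1.23 (s = 2), 1.05-1.10 (s = 3) and 1.03-1.06 (s = 4). ANCOVA residual variances gave the same ratios to within 0.001, so adjusting for baseline does not recover the loss. Recorded height differed between two visits in 23-51% of simulated participants.

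**Step 3: where the height part comes from.** At s = 1.5 and e = 0.5, the 39% splits into:
- weight rounding, 7.4%
- height re-measurement, 0.128 × 0.5/0.269 = 23.8%
- height rounding, 0.128 × 0.1667/0.269 = 7.9%

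At the top of the range, re-measurement error dominates. With e = 0 the two rounded heights would be identical and the height part would be zero; the formula in Step 2 does not hold at that limit.

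**Step 4: meaning for the trial.** Variance inflation of 5-40% widens the standard error by √1.05 − 1 = 2.5% to √1.40 − 1 = 18%. In the s = 2, e = 0.3 case (simulated ratio 1.137), the equivalent loss is 60 × (1 − 1/1.137) = 7.2 participants per arm for this endpoint. Weight rounding alone at s = 2 costs 60 × (1 − 1/1.042) = 2.4.

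**Step 5: after the fix.** With one Visit 3 height and weight to 0.1 kg (an assumed scale resolution), inflation is (0.01/6)/s², which is 0.07% at s = 1.5 and less above that.

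**The case against.** A reader might infer that BMI change in this trial does carry a 5-40% variance penalty. The documents do not support that. Neither one says that same-visit height enters follow-up BMI. The longitudinal BMI analysis is described in terms of weight measurements only, and its phone-weight extension has no height of its own; both fit a single carried height. The SAP baseline table takes height from the Visit 3 form, though a baseline table would do so in any case. If one height is intended, only the weight-rounding part remains. This objection stands, and it makes the height part a conditional finding.

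A reader might also blame the 1 cm rule. That is only partly right, as Step 3 shows. Once height is fixed, its rounding adds almost nothing to the variance of change, so a finer height recording is not needed for this purpose.

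The range itself rests on assumed SDs. The 40% needs the smallest weight-change SD together with the largest height error; if weight change is more variable, the effect is small. The 7-participant equivalent is one cell of the grid.

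Finally, the error does not depend on arm, BMI is one of more than 20 secondary endpoints in a pilot, and weight is analysed separately and is immune to height error. All of this is fair and limits the importance of the point. It does not remove it: the whole-kilogram rule is explicit, the height rule is missing, and both are nearly free to settle.

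**Conclusion.** The point holds as a loss of precision and a gap in the derivation. Certain from the text: weight is rounded to whole kilograms, height is re-measured at four clinical visits, and the height used for follow-up BMI is unspecified.

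Weight rounding by itself inflates the variance of weight and BMI change by about 2-7% for a weight-change SD of 3 to 1.5 kg, and about 1% at 4-5 kg. If same-visit height is used, the total for BMI is about 5-40% for weight-change SD 1.5-3 kg and height repeatability SD 0.2-0.5 cm, and about 2-6% at weight-change SD 4-5 kg. None of these SDs is in the documents.

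There is no bias between arms and no effect on the primary endpoint, so this should not be read as a threat to the trial's main conclusion.

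**What to change.** In SAP 1.16:

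1. Record weight at the resolution that the scale displays, without rounding to whole kilograms.
2. State that BMI at every time point, including BMI from phone-reported weights, is computed with the single Visit 3 height. Heights from Visits 6, 8 and 10 serve only as a data check.

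The cost is an SAP edit and an eCRF edit. The protocol visits can stay as they are; removing height from later visits would need a protocol amendment and gains nothing here. Rule 2 can be applied to data already collected. Rule 1 cannot restore precision to weights already recorded in whole kilograms, so weight resolution may be mixed; if so, the date of the change should be documented.
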